**Form A**

IRB #	STU -----
-------	-----------

*Table 1.* Summary of instrumentation with objectives, measures and distribution plan. Summary of data analysis plan per primary and secondary objectives. Minimum detectable difference between two study arms with 80% power at 2-sided significant level of 0.05 (n=100 per arm)

Aims	Objective Type	Instrumentation	Outcome Measure	Distribution	Minimum Detectable Effect Size at 80% power
Aim 1: Patient Satisfaction	Primary	GCSS	Whole scale score	Post	+/-0.8 points, assuming SD = 2 
Aim 1: Knowledge	Primary	MMIC (8 knowledge questions)	Measure score difference from pre/post	Pre and Post	+/-2 points, assuming SD = 5.03
Aim 1: Informed Decision Making	Second	MMIC (entire measure)	Measure score difference from pre/post	Pre and Post	n/a
Aim 1: GC-specific empowerment	Second	GOS	Measure score difference pre/post	Pre and Post	+/-18.54 points, assuming SD = 46.58 
Aim 2: GC visit completion	Primary	Database query	Proportion of visits scheduled and completed	n/a	18.6%, assuming 63% in control group 
Aim 2: Genetic test completion	Second	Database query	Proportion of genetic tests completed w/n 60d of visit	n/a	19.4%, assuming 77.4% in control group 
Aim 2: Genetic test cancellation/failure	Second	Database query	Proportion of genetic tests initiated compared to tests canceled/failure	n/a	15%, assuming 9% in control group 

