#### 1. Purpose and objectives. *List the purpose and objectives:*

The overarching goal of this pilot prospective randomized controlled study is to compare patient-reported and clinical operations outcomes between in-person genetic counseling (IPGC – control) and telephone-based genetic counseling (TGC – intervention) in an indigent English or Spanish-speaking population seeking genetic counseling for hereditary cancer syndromes to create a framework for effective and efficient genetic service delivery in these populations nationally. General genetic education and principles will be conveyed through a standard genetic counseling session including a pre-test education video in both the TGC and IPGC arms. Our primary project objectives are to compare the following outcomes between the IPGC and TGC study arms. Aim 1: Patient reported outcomes – A. Patient satisfaction with genetic counseling visit; B. Knowledge of basic principles of cancer genetics and implications of genetic testing for personal healthcare and relatives. Secondary objectives for this aim are: 1. Patient ability to make informed choice; and 2. Genetic counseling-specific empowerment outcomes. Aim 2: Clinical outcomes – visit completion rate; Secondary objectives are: 1. Genetic testing completion rate; and 2. Genetic testing cancellation/failure rate. We hypothesize that patients in the TGC arm will not have significant differences in knowledge, satisfaction, informed choice or genetic counseling-specific empowerment compared to the IPGC arm. We also expect significantly increased visit completion rate and lower test completion rate in the TGC arm compared to the IPGC arm, but no significant difference in sample failure rate.

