Data Analysis. Our primary study outcomes are to compare change in knowledge pre and post visit (through MMIC knowledge questions), patient satisfaction with GC visit after completion (GCSS) and genetic counseling visit completion rate between IPGC and TGC. Secondary objectives include comparison of empowerment score (GCOS), informed choice (MMIC scale), genetic testing completion, and cancelation/failure rates between the arms.

To evaluate intervention effects, we will conduct univariable and multivariable analysis for comparisons of each outcome of interest between intervention (TGC) and control group (IPGC). For the survey data, we will examine the data from each survey as well as total score or overall index of multiple questionnaires and compare them between the two study arms. We will perform linear regression models for continuous outcomes (e.g., total score of questionnaires) and logistic regression models for binary outcomes that are based on binary response (e.g., visit completion rates, test cancelation/failure and test completion rates). To compare binary outcomes between arms (such as visit completion rate), we will test by comparing rates of each arm via Chi-squared analysis and control for potential confounders. Potential covariates under consideration (e.g., age, race, sex, language, etc.) will be assessed as necessary and adjusted in multivariable models accordingly. We will evaluate whether there is any evidence of multi-collinearity issues among these variables to be adjusted in the model. Possible effect modifiers of intervention effects will be also evaluated by testing interactions (e.g., sex) and addressed to develop the final multivariable models, as well as reporting the intervention effect stratified as an effect modifier. Underlying assumptions of aforementioned regression models including linearity of associations will be also evaluated. We will examine dropouts or missing data to be able to identify accurate missing data mechanisms and select the best statistical approach. All analyses will be performed using SAS 9.4 (SAS Institute Inc, Cary, NC) at a statistical significance level of  $p=0.05$ .

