We anticipate a post-enrollment dropout (failure to complete the surveys) rate of 30% given our work with the underserved population. We plan to enroll 280 patients at a 1:1 ratio per arm (100 individuals enrolled per arm), expecting 200 to complete measured responses. We will monitor the dropout rate after the initial 50 individual responses are completed and adjust accrual for study-specific dropout until we have 200 participants' complete measured responses. With 200 patients we will enroll, we can detect mean differences of 0.398 standard deviation (SD) between two study arms with 80% power at a significance level of 0.05 (Table 1). For example, assuming SD of 2 for the GCSS, we will be able to detect a minimum difference of 0.8 ( $=0.398*2$ ) between two study arms with 100 participants enrolled per arm. For GCOS, assuming SD of 46.58, we will be able to detect a minimum difference of 18.54 between pre- and post-visit scores. For visit completion as the primary binary outcome variable, we will be able to detect a minimum difference of 18.6% assuming 63% in the control group, e.g., 81.6% (intervention) vs. 63% (control) with 80% power at significance level of 0.05. Of note, previously published outcomes and unpublished internal data will serve as a baseline for the study population.

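### Genetic test completion appears to be counted per visit, and TGC is expected to raise visit completion, so the comparison could show TGC as worse when as many or more scheduled patients are tested

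*Combined protocol and SAP*

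**What the plan says.** Table 1, Aim 2, gives the test-completion measure as "Proportion of genetic tests completed w/n 60d of visit" and its detectable effect as "19.4%, assuming 77.4% in control group", for 100 patients per arm, 80% power and a two-sided 5% level. The row above it makes visit completion a primary outcome, measured as "Proportion of visits scheduled and completed". The sample-size paragraph in section 4.a illustrates that outcome with "81.6% (intervention) vs. 63% (control) with 80% power". Section 1 gives the expected directions: "We also expect significantly increased visit completion rate and lower test completion rate in the TGC arm".

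The Data Analysis paragraph in section 4.a names logistic regression and chi-squared comparisons for the binary outcomes but gives no analysis population for test completion. Under Genetic Counseling and Genetic Testing, patients who do not complete testing stay in the study. Nothing there or elsewhere says how a patient who misses the visit is counted.

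**The concern.** Attendance happens after randomisation and, on the plan's own hypothesis, depends on the assigned arm. If only attenders can be counted, patients who would keep a telephone visit but miss an in-person one enter the TGC denominator and have no counterpart in the control denominator. They may well be less likely to finish testing. The two sets of attenders then differ for reasons other than what counseling does to test completion. Adjusting for age, race, sex and language cannot be relied on to remove that difference.

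The stated goal is a framework for service delivery, for which the share of scheduled patients who end up tested matters. A per-visit rate can move in the opposite direction to that share. Because section 1 already predicts lower test completion with TGC, such an artefact would read as confirmation of a hypothesis.

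**Working it through.** **Inputs.** Control visit completion 63%; TGC visit completion 81.6% (example in the sample-size paragraph); control test completion 77.4%; detectable difference 19.4 points; 100 per arm; two-sided 0.05; 80% power.

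**1. Reproduce the plan's figure.** Take 77.4% against 77.4 - 19.4 = 58.0%, with mean 67.7%:

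n = [1.960·√(2·0.677·0.323) + 0.842·√(0.774·0.226 + 0.580·0.420)]² / 0.194², which is just over 90, so 91 per arm.

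With continuity correction, n' = (n/4)·[1 + √(1 + 4/(n·0.194))]², which is just over 100, so 101 per arm. Solving for the difference at exactly 100 per arm gives 19.4 points downward and 15.1 points upward. The 19.4 is therefore right, and it is the figure for a lower TGC rate, in line with section 1. The same method gives 18.6 points for visit completion, also as stated.

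**2. Which denominator do the planning rates imply?** If testing follows a visit and both control rates describe the same patients, at most 63% of scheduled control patients can be tested. A rate of 77.4% cannot then be a share of scheduled patients; it must be a rate among those who had a visit, or some subset of them.

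**3. Equal share tested.** Let v be visit completion, t the tests per completed visit, and s = v × t the share of scheduled patients tested. Control: s = 0.63 × 0.774 = 48.8%. If TGC also tests 48.8%, its per-visit rate is t = 0.4876 / v:

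| TGC visit completion | TGC per visit | Gap to 77.4% |
|---|---|---|
| 70% (assumed) | 69.7% | -7.7 points |
| 75% (assumed) | 65.0% | -12.4 points |
| 81.6% (detectable value) | 59.8% | -17.6 points |
| 90% (assumed) | 54.2% | -23.2 points |

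At 81.6%, the chance of a significant result against TGC (two-sided 0.05, uncorrected test) is about 62% with the 63 and 82 attenders expected from 100 scheduled per arm, and about 77% with 100 attenders per arm.

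**4. More patients tested with TGC.** At 81.6% attendance the additional attenders are 0.816 - 0.63 = 0.186 of those scheduled. Suppose they complete testing at rate r and the others at 77.4%. Then s = 0.4876 + 0.186·r and t = s / 0.816:

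| r (assumed) | TGC share of scheduled tested (control 48.8%) | TGC per visit (control 77.4%) |
|---|---|---|
| 0% | 48.8% | 59.8% |
| 25% | 53.4% | 65.5% |
| 50% | 58.1% | 71.2% |
| 77.4% | 63.2% | 77.4% |

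In the middle rows TGC tests more patients yet reads as worse. In the last row a gain of 63.2 - 48.8 = 14.4 points reads as no difference.

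**The case against.** The denominator is inferred. The 60-day phrase sets a time window, the unit is tests, and the next row of Table 1 refers to tests initiated, so the denominator could be tests ordered. That stands as a limit on the arithmetic: 0.63 × 0.774 would then also need an ordering rate, which the documents do not give. It does not remove the problem, since an order also follows a visit. The comparison of 77.4% with 63% assumes one population; the two rates carry the same citation number, but the source cannot be checked here.

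It is also fair that visit completion is reported alongside as a primary outcome, so a careful reader could combine the two, and that the per-visit rate answers a legitimate question about counseled patients. Both support keeping the per-visit rate, but not as the between-arm comparison.

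Two stronger inferences are tempting. A reader might multiply 81.6% by 58.0% to get 47.3%, against 48.8% in control, and conclude that the planned effect shrinks to 1.4 points. The documents do not support this: 81.6% is a detectable value introduced as an example, 58.0% is not written anywhere and is only the control rate minus a detectable difference, and pairing two limits computed at the same sample size is not a forecast. A reader might also infer that the trial will conclude that TGC lowers test completion. It could; whether it does depends on how the additional attenders behave, and the artefact disappears if they complete testing at 77.4%.

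Finally, changing one denominator does not by itself restore a randomised comparison. Randomisation precedes the eligibility call and consent, and section 4.a then removes switchers, unreached patients, decliners and those with missing surveys or video. This stands, and the fix has to address it.

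**Conclusion.** The point holds as a gap in definition with a foreseeable bias. As most plausibly read, test completion is conditional on attendance, a primary outcome that the intervention is expected to raise. On the plan's rates and the assumptions stated in the working (one population, every attender a candidate for testing, TGC attendance between 70% and 81.6%), an equal share tested would appear as a TGC deficit of 7.7 to 17.6 points. The 19.4-point detectable difference is correctly computed; the weakness is what it is a difference in. The outcome is secondary, so this is a worthwhile improvement and not a threat to the primary comparisons.

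**What to change.** - Define the between-arm test-completion outcome as the proportion of all randomised and scheduled study patients, analysed by assigned arm, with a completed test within a fixed window from the scheduled visit date. Count non-attenders as not tested.
- State which post-randomisation exclusions apply. Do not apply the post-visit ones (video not viewed, post-appointment survey missing at one week) to this outcome. If data on patients who declined or were not reached cannot be used, take all consented patients with a scheduled visit and state that limit.
- Keep the per-visit rate as a descriptive supporting result, with its denominator written out.
- Restate the Table 1 row. With a control rate of about 48.8% and 100 per arm, the detectable difference with continuity correction is about 20 points (20.4 upward, 20.2 downward) instead of 19.4.

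The cost is SAP wording, a slightly larger detectable difference, and a check that the database query covers non-attenders. That check is needed because test completion is not among the items that Randomization and Scheduling lists for all referred patients.

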## Form A

IRB #	STU -----
-------	-----------

SC will attempt to contact patients who cannot be reached the following business day.

Patients who do not complete pre-appointment survey will be excluded from study but will continue with scheduled genetic counseling appointment as standard of care.

Pre-appointment survey completion status and survey completion method will be recorded in RedCap by SC.

Genetic Counseling and Genetic Testing. Patients who are unable to watch the educational video prior to, or during their genetic counseling visit will be excluded from the study. They will still continue with their appointment, but not through the study. Patients excluded for this reason will be recorded in RedCap by SC.

Sample failure and test completion status will be recorded in RedCap by SC. Failure to complete testing will not exclude patient from the study itself.

Post-Appointment Survey and Study Incentive. SC will send post-appointment survey within 24 hours of GC appointment. A Spanish version of the survey will be sent to Spanish-speaking patients.

The post-appointment survey will consist of the Multi-dimensional Model of Informed Choice (MMIC) assessment, the Genetics Outcome Scale (GOS) and the Genetic Counseling Satisfaction Scale (GCSS).

SC will monitor survey completion status. Those with incomplete post-appointment surveys will receive reminder two business days post-appointment and will be offered option to complete the survey via telephone with SC.

If patient is not reached, SC will attempt to contact patient the following day (three business days post-appointment).

Those with incomplete surveys one week after the genetic counseling appointment will be excluded from study. This data will be recorded in RedCap.

Those who complete study surveys will be sent a \$15 gift card electronically.

Location/Setting. For IPGC, patients will be seen within PHHS/JPS clinics. Spanish translation services are provided through PHHS and JPS for patients in their institutions. TGC patients will not be required to be in a certain environment, but we anticipate they will be in their homes or workplace in a secure, private location. GCs will either be in a HIPPA compliant setting offsite or within a UTSW workspace for TGC visits.

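### The hypothesis is about sample failure, but the only planned outcome pools failed with cancelled tests, so its result cannot be attributed to sample failure

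*Combined protocol and SAP*

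**What the plan says.** Section 1 (Purpose and objectives) lists among the Aim 2 secondary objectives the "Genetic testing cancellation/failure rate". The hypotheses at the end of the same section use a narrower term. They expect "lower test completion rate in the TGC arm compared to the IPGC arm", "but no significant difference in sample failure rate".

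The Data Analysis text in section 4.a treats cancellation and failure as one binary outcome for logistic regression, in the list "visit completion rates, test cancelation/failure and test completion rates", with chi-squared comparison of rates between arms. Table 1 gives this outcome one row, with the measure "Proportion of genetic tests initiated compared to tests canceled/failure" and the detectable difference "15%, assuming 9% in control group". The row for test completion, counted within 60 days of the visit, reads "19.4%, assuming 77.4% in control group". Table 1 gives a database query as the source for both rows.

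On data capture, the paragraph on genetic counseling and testing in section 4.a says: "Sample failure and test completion status will be recorded in RedCap by SC". Cancellation is not named there. No section defines a cancelled test, gives a failure-only rate, or explains why completion should be lower with telephone counseling (TGC) than in person (IPGC).

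**The concern.** The hypothesis has no outcome of its own. A pooled rate has two components, and the hypothesis is about one of them. A difference in the pooled rate could be read as poorer samples with TGC when it reflects orders that were cancelled. A pooled null could hide more failed samples offset by fewer cancellations: an assumed 3% failed + 6% cancelled in one arm and 6% failed + 3% cancelled in the other both give 9%.

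The plan's own expectations make this more than a matter of wording. A test cancelled and not replaced within 60 days also counts as not completed, so the pooled outcome overlaps with test completion, where section 1 expects the arms to differ. Failed samples and cancelled orders are also different operational problems for a study meant to guide service delivery.

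**Working it through.** **Inputs from Table 1.** Control cancellation/failure 9%, detectable difference 15 points; control test completion 77.4%, detectable difference 19.4 points; 100 per arm, two-sided 0.05, 80% power.

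**Step 1: reproduce the plan's figures.** Normal approximation with pooled variance under the null, p̄ = (p1 + p2)/2:

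power = Φ{ [ |p2 − p1|·√n − 1.96·√(2p̄(1 − p̄)) ] / √(p1(1 − p1) + p2(1 − p2)) }

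For 9% vs 24%, p̄ = 0.165:
- √(2 × 0.165 × 0.835) = 0.525
- √(0.09 × 0.91 + 0.24 × 0.76) = 0.514
- (0.15 × 10 − 1.96 × 0.525)/0.514 = 0.92, so power is 82.0%.

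Solved for the difference at 80% power, this gives 14.6 points, or 15.8 with continuity correction. Fisher's exact test has 78.5% power for 9% vs 24%. The stated 15 points is accepted as a rounded figure. The completion figure (77.4% vs 58.0%) matches with continuity correction: 19.4 to 19.5 points, 101 per arm.

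**Step 2: pooled outcome with identical sample failure.** Assume that TGC completion is lower by Table 1's 19.4 points, that both outcomes are counted over the same 100 tests per arm, and that a share s of the extra non-completion is coded as cancelled. The share s is not in the documents. The pooled TGC rate is then 9% + s × 19.4%, and the formula above gives the chance of a significant pooled difference:

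| s | Pooled TGC rate | Chance of p < 0.05 |
|---|---|---|
| 0 | 9.0% | about 5% |
| 0.25 | 13.9% | 19% |
| 0.50 | 18.7% | 51% |
| 0.75 | 23.6% | 80% |
| 1 | 28.4% | 95% |

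The result does not depend on how the control 9% splits into failed and cancelled, because failure is held equal.

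**Step 3: what Table 1 implies about s.** Control non-completion is 100 − 77.4 = 22.6%. If the denominators match, at least 22.6 − 9 = 13.6 points are neither cancelled nor failed, so at most 9/22.6 = 40% of control non-completion is cancelled. If the extra TGC non-completion followed the same pattern, s would be at most about 0.4, between the 0.25 and 0.50 rows. Nothing says that it would follow that pattern.

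**Step 4: sample failure alone.** Detectable increase at 100 per arm, without continuity correction, for assumed control failure rates (the documents give none):

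| Control failure | Detectable increase |
|---|---|
| 1% | 9.0 points |
| 3% | 11.0 points |
| 4.5% | 12.1 points |
| 6% | 13.1 points |

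These grow if fewer than 100 tests per arm are initiated. The pooled outcome shows the scale: with an assumed 70 per arm its detectable difference rises from 14.6 to 18.1 points.

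**The case against.** The strongest reply is that sample failure is simply shorthand. Section 1 lists three clinical outcomes and then three predictions in the same order, so the third prediction lines up with cancellation/failure. The two testing items that the coordinator records likewise line up with the two testing rows of Table 1. This reading is plausible, but no section says so. If it is right, aligning the wording is enough.

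A reader might infer that lower completion with TGC would necessarily raise the pooled rate. The documents do not support that. They never link non-completion to cancellation, and Step 3 shows that much of it in the control arm need not be cancellation. If completion is counted per visit or per patient, tests never initiated would lower completion without entering the pooled outcome. Only could raise is justified.

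A reader might also infer that the hypothesis cannot be examined at all. That goes too far: sample failure status is to be recorded, so a failure-only comparison appears possible from data already planned. Nor does the coordinator's list prove that cancellations go uncaptured, since the database query may supply them. What stands is that the analysis text and Table 1 plan only the pooled comparison.

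Finally, this is one secondary outcome in a pilot. That limits its weight but does not remove the mismatch.

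**Conclusion.** The concern holds for the outcome as defined. The hypothesis names sample failure, the planned outcome pools it with cancellation, and neither a pooled difference nor a pooled null can be attributed to sample failure. With identical sample failure, the chance of a significant pooled difference runs from about 5% to 80% as the share of extra non-completion coded as cancelled goes from 0 to 75%. That range rests on three assumptions: a completion gap equal to Table 1's 19.4 points, common denominators, and 100 tests per arm. It is an illustration, since the documents give neither the share nor the expected size of the completion gap.

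**What to change.** In the Data Analysis text and Table 1:
- Define a failed sample and a cancelled test, and report them as two outcomes, both over tests initiated.
- Tie sample failure to the section 1 hypothesis, and read cancellation alongside test completion.
- Keep the pooled rate as descriptive.
- Record cancellation as its own REDCap item if the database query does not already capture it.

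Tests initiated is the better denominator. Samples received by the laboratory would be a further subset formed after randomization, could differ by arm, and is not described as recorded.

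If sample failure was meant as shorthand for the pooled outcome, restate the section 1 hypothesis for the pooled rate instead.

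The cost is a Table 1 edit, two definitions and at most one added REDCap item. The downside is precision. Failure alone is rarer, so its detectable difference must be restated (about 9 to 13 points for assumed control rates of 1 to 6% at 100 per arm, larger with fewer tests initiated) or the comparison called descriptive. No primary analysis or sample size changes.
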